On three evenings over the next 7 days, the children will eat a standard high protein/high fat meal. The evenings will not be set, but will depend on the child and family schedule. The study meal will not be eaten on the evening that the CGM is inserted as sensor accuracy takes 24 hours to maximise accuracy. The child and family will be able to choose which days during the study period on which they complete the study meals but will be advised to avoid days when the participant has undertaken lots of exercise, is hypoglycaemic immediately before the meal or has had frequent hypoglycaemic episodes, or has been unwell.

The standard meal will be a portion controlled gluten-free meal provided and delivered by Wiltshire Farm Foods consisting of a meat-based main course and dessert. These will be kept frozen until used by participants and prepared according to manufacturer instructions. These meals come in two sizes which allow portion sizes to be adjusted for different ages of child, but the proportions of fat, protein and carbohydrate will be kept constant for each child, and by definition the meals will be high in protein and high in fat.

Insulin doses with the standard meal will be given according to calculations carried out by the dietitian and administered in one of three ways.

The three evenings in random order will be as follows -

1. Insulin units based on ICR and fat/protein dose given together immediately before the meal [control meal].
2. Insulin units based on ICR given immediately before the meal plus extra insulin for fat/protein units given 1 hour after the first meal dose.
3. Insulin units based on ICR given immediately before the meal plus extra insulin for fat/protein units given 2 hours after the first meal dose.

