Participants will be asked not to give a correction dose before the meal if the BG level is between 7-12mmol/l as this would interfere with the analysis. They will be asked, if possible, not to carry out the test meals if their pre-meal BG is greater than 12 mmol/l. But if they have to do the test meal with a high pre-meal BG (above 12 mmol/l) they will be instructed to give their usual correction bolus in addition to the prescribed insulin dose for the test meal. This data will be analysed separately. If BG is below 4mmol/l (hypoglycaemic) or above 16mmol/l participants will be asked to abandon the study evening and repeat on another evening. Full written instructions will be provided to the family for all aspects of the insulin dosing for the study meals.

During the study on the standardised meal days children will be instructed not to eat any food after the meal during the evening, and not to correct any later BG levels unless they are dangerously high (BG over 16 mmol/l with ketones over 0.5 mmol/l). If BG levels go low at any time (BG less than 4 mmol/l) children will be instructed to treat the hypoglycaemia according to their usual management, and omit

any further study doses of insulin if the hypoglycaemia occurs after a first study dose and a second is due. This data will be analysed separately. Children and families will be asked to complete diaries during the trial week.

At the end of the study period (the day after the third meal), children will come back to the research facility or clinic for the end of study visit (visit 3). A research nurse or dietitian will remove the CGM sensor and download the data onto a secure laptop. Children and their families will then be asked to complete a short questionnaire about the acceptability of using the extra insulin doses, and their perceptions as to whether there were any beneficial or adverse effects.

The study dietitian will calculate standard outcomes from each patient's sensor download and pass on anonymously to the study statistician to analyse the data.

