8.3. Randomisation, blinding and code-breaking

Randomisation is required only for the order of the insulin dosing. The study statistician will provide the randomisation codes and the study dietitian will make up sealed envelopes with all the instructions inside for the schedule for the participant according to the randomised order of treatment. This schedule will form part of the study diary for each participant. The envelopes will be kept in the research office in Oxford until they are needed, when the next one will be taken for the next participant entering the study at any of the participating sites. The envelope will be opened by the research nurse or dietitian at the first study visit when the CGM is being inserted. As the same research team will be working at all sites there is no requirement for separate codes for each site.

Unblinding will not be required as this is not a blinded study. Participants and researchers will know the order of the insulin doses for the test meal from the start of the study.

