8.5. Subsequent Visits

Visit 2 – Study visit

- A review of the BG levels in the preceding week will be carried out by the study dietitian, in order to determine whether any further adjustments in insulin dose need to be made.
- The CGM will be inserted.
- Randomisation of the insulin dose order will be carried out and final dose calculations will be done by the dietitian according to the equations in section 5.3.
- Full written instructions will be provided to the participants, including insulin doses and timings for the three study meals, contact details and what to do if BG levels should be high (greater than 16mmol/L) or low (less than 4mmol/L).
- There will also be instructions about what they should do in the event of a sensor malfunction.
- The child and family will be informed that they can call the research team during office hours at any stage to discuss events during the week of the study, and they will be provided with contact details. If any advice is required outside office hours, they will be advised to contact their clinical diabetes team in the usual way.

Visit 3: End of study visit - The participant will return to their original outpatient or day-care setting and the CGM sensor will be removed by the study nurse and data downloaded onto the web-based system Diasend which is regularly used in clinics. Participants and their family will have the opportunity of viewing the download from the sensor. The participant and parent will be asked to complete the short questionnaires about the acceptability of the additional insulin doses.

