9.3. Compliance with Trial Treatment

Participants and their families will be asked to complete a diary including the actual insulin doses given. This will be viewed at the end of the study and data may be removed from analysis if significant non-compliance has occurred, for example the advised dose was not given, or the timing was not accurate to within 15 minutes.

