11.4. Criteria for the Termination of the Trial

We would only anticipate 10 episodes of severe hypoglycaemia in 340 patients per year. Therefore the likelihood of a severe hypo occurring during this study under normal circumstances would be very small. So if we assume there is no increase in risk then we would only expect to see 2 severe hypos in one of the two arms in 3 out of every 10,000 trials, for a single hypo in either arm this increases to about 1 in every 100 trials. Therefore we would terminate the trial if we had 2 severe hypos occurring on any arm of the trial.

11.5. Procedure for Accounting for Missing, Unused, and Spurious Data.

We will use boxplots to identify outlying, unusual or spurious data using pre-defined decision rules (e.g. upper or lower quartiles $\pm 1.5 \times \text{IQR}$). In the case of implausible or unlikely outcome data we will look back at CRF's to rule out data handling errors. If outliers cannot be resolved then we will exclude this particular result from the main analysis. We intend to use a complete case analysis but we will conduct a sensitivity analysis to assess the impact of any missing data using appropriate multiple imputation methods.

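### Outcome derivation and open-ended exclusions can be done by people who know the insulin timing: the plan anonymises the data but is not said to mask the condition

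*Combined protocol and SAP*

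**What the plan says.** **Who derives the outcomes.** Section 6.3: "The study dietitian will calculate standard outcomes from each" participant's "sensor download and pass on anonymously to the study statistician to analyse the data". Section 11.1 has the chief investigator, the research dietitian and the statistician all analysing the continuous glucose records. It does not say who does which part.

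**Who knows the order.** Section 8.3: the statistician supplies the randomisation codes and "the study dietitian will make up sealed envelopes with all the instructions inside". The study is declared unblinded: "Participants and researchers will know the order of the insulin doses for the test meal from the start of the study".

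**Which decisions are open.**
- Section 9.3: "data may be removed from analysis if significant non-compliance has occurred". A dose not given and a 15-minute timing tolerance are offered as examples.
- Section 11.5: outlier rules are called pre-defined, but the boxplot fence (1.5 times the interquartile range) is given only as an example. "If outliers cannot be resolved then we will exclude this particular result from the main analysis".
- Section 11.6: data after a protocol breach are not used for that meal. Extra food is one example of a breach, and the list is not closed.

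**Which decisions are fixed.** Under section 11.6, data after a glucose below 4.0 mmol/L, or after additional insulin for a high value, are analysed separately. Section 6.3 separates meals started above 12 mmol/L with a correction dose.

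No section says who makes the open decisions, that they are settled before the condition is known, or that a second person repeats the derivation.

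**The concern.** The comparison is between three timings of the same additional dose, within the same child. Dosing has to be open. Deriving outcomes and excluding data do not, apart from checking dose timing. If whoever drops a meal or an outlying value knows which timing it belongs to, exclusions can lean towards one timing without any intent to do so. With 36 to 40 children, a few such decisions in one direction could matter. As the plan stands, a reader of the results could not rule this out.

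**Working it through.** **1. Masking, step by step.** There is no plan figure to reproduce, so the sections are set side by side.

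| Step | Who | Condition hidden? |
|---|---|---|
| Codes generated (8.3) | Statistician | No |
| Envelopes made up (8.3) | Dietitian | No |
| Outcomes calculated (6.3) | Dietitian | Not stated |
| Glucose records analysed (11.1) | Chief investigator, dietitian, statistician | Not stated |
| Non-compliance removal (9.3) | No role named | Not stated |
| Outlier exclusion (11.5) | "We" of the statistics section, no role named | Not stated |
| Breach handling (11.6) | No role named | Not stated |

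Section 8.3 says that researchers know the order, so whoever decides can know the condition. The outlier check goes back to the CRFs. Section 12.1 says CRF data come from the diaries, and section 8.3 puts the randomised schedule in the diary. The look-back itself can therefore reveal the timing.

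**2. Would the outlier rule come into play?** Assume normal data and the 1.5 x IQR fence. Simulated samples of 36 values contain 0.57 flagged values on average, and about 35% contain at least one. The decision would arise in practice.

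**3. Illustration of scale, on assumed inputs.** Removing *m* of *n* paired differences that lie on average *d* from the mean, all on one side, shifts the mean by *m* x *d* / (*n* - *m*). The documents give no *d*. With *n* = 40:

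- *d* = 2 mmol/L: 2/39 = 0.05 for one, 6/37 = 0.16 for three.
- *d* = 5 mmol/L: 5/39 = 0.13 for one, 15/37 = 0.41 for three.

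For a worst case, section 11.2 (36 children, 80% power, 2 mmol/L, 5% level) can be back-solved for the SD of a paired difference. This assumes a two-sided test of one paired contrast. The normal approximation gives 2 x √36 / (1.960 + 0.842) = 4.28 mmol/L, and the noncentral t gives 4.16. If the 5% were split over three contrasts, the t-based value would be 3.56. With no true difference and normal data, the *m* least favourable differences were dropped, always on the same side (100,000 simulated trials per row, SD 4.16):

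| Dropped of 40 | Mean shift, mmol/L | Two-sided 5% test rejects |
|---|---|---|
| 0 | 0.00 | 4.9% |
| 1 | 0.23 | 7.5% |
| 2 | 0.43 | 12.4% |
| 3 | 0.61 | 19.0% |
| 4 | 0.78 | 27.2% |

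The rejection rates do not depend on the SD. The shifts scale with it: for three dropped, 0.61 x 3.56/4.16 = 0.52 to 0.61 x 4.28/4.16 = 0.63. This describes systematic removal of the worst values, which nothing in the documents suggests will happen. The 2 mmol/L also refers to the 5-hour excursion, whereas the primary outcome is over 8 hours.

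**The case against.** **The outcome is recorded automatically.** CGM stores a value every 5 minutes, and summarising a clean trace is arithmetic. The main truncation points follow fixed rules in section 11.6. This stands, and it limits the point to the open decisions and to derivation choices that the text leaves unstated, such as time zero and sensor gaps.

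**The dietitian decides the exclusions.** A reader might infer this from section 6.3. The documents do not say so. Section 9.3 names no one, and section 11.5 speaks for the team in a section written by the statistician. The point rests on the whole team being unmasked, not on one person's role.

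**The statistician sees only derived values and could never detect a poor decision.** Section 6.3 alone might suggest this. Section 11.1 contradicts it by giving the statistician a role with the glucose records, and section 11.5 provides for a check against the CRFs. Neither hides the condition, and the statistician generated the codes.

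**Calculating the doses adds to the danger.** It is true that "Insulin doses with the standard meal will be given according to calculations carried out by the dietitian", and at Visit 2 "final dose calculations will be done by the dietitian". But one algorithm sets each child's doses, and the three evenings differ only in when the fat and protein dose is given. Setting the amount gives no route to favour one timing.

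**Compliance cannot be judged blind.** This is correct. Whether a second dose was given on time depends on which timing was assigned.

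**Section 11.5 plans a multiple-imputation sensitivity analysis.** That addresses missing data. It does not govern who decides what is excluded.

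**Conclusion.** The point holds in a limited form. An unmasked role derives the outcomes, the hand-over is not said to hide insulin timing, and three exclusion rules are open enough to need judgement, with no named decision-maker and no lock before the condition is known. Sections 6.3 and 11.1 also need reconciling on who derives and who analyses.

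The bias cannot be sized from the documents. The figures above rest on an assumed distance *d*, or on normal data, a back-solved SD and deliberate one-sided removal. They show only that a handful of exclusions could matter in a trial of this size. A reader might infer from the table that the type I error is inflated to those levels. The documents do not support that, because they show neither that exclusions will be one-sided nor how many there will be. This is a cheap improvement to the conduct of the analysis, not a flaw that invalidates the design.

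**What to change.** 1. **Relabel before derivation.** An existing team member other than the statistician, such as the research nurse who already downloads the sensor under section 8.5, exports the 5-minute CGM data and meal times under new participant and meal labels. The labels must hide both timing and order, so calendar dates should be dropped too. Include the times of hypoglycaemia treatment, extra insulin and extra food that section 11.6 needs, but not the study-dose times. New labels are necessary because the statistician produced the original codes.
2. **One prespecified script** derives every outcome, with time zero, baseline and sensor-gap handling written down beforehand.
3. **Fix and lock.** Replace the example outlier rule with a definite one and close the list of breaches. List the trace-usability and outlier decisions and lock them before labels are linked to timing. The holder of the labels does the CRF look-back and reports only whether a data-handling error was found.
4. **Compliance.** Apply the dose-given and 15-minute criteria of section 9.3 as a fixed rule, without reference to the glucose outcomes, and report exclusions by condition. The control meal has no delayed dose to mistime, so these exclusions may fall unevenly even when applied fairly.
5. **Reconcile sections 6.3 and 11.1** on who derives the outcomes and who analyses them.

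Cost: some scripting and file-preparation time from existing staff. Some unmasking may remain, because the shape of a trace can hint at the timing. Dosing, visits and participant burden do not change.

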7. PARTICIPANT IDENTIFICATION

7.1. Trial Participants

Children and young people aged between 6 and under 18 years with Type 1 diabetes on multiple insulin injection regimes who are under regular out-patient review by the Oxfordshire Children's Diabetes Service or the Royal Berkshire Children's Diabetes Service.

7.2. Inclusion Criteria

- Diagnosis of Type 1 diabetes (for at least a year)
- Aged 6 to under 18 years.
- On multiple daily insulin injections, including basal long-acting insulin and rapid-acting insulin before each meal.
- HbA1c < 75 mmol/mol (9.0%)
- Participant and/or parent/legal guardian willing and able to give informed consent for participation in the study.
- Family have a freezer in which to safely store the test meals.
- In the Investigator's opinion, is able and willing to comply with all trial requirements.

7.3. Exclusion Criteria

The participant may not enter the trial if ANY of the following apply:

- HbA1c greater than 75 mmol/mol (9.0%)
- Child unwilling to agree to second insulin injection at a meal-time
- Untreated coeliac disease or other concomitant condition likely to affect BG control
- Food allergies (other than controlled Coeliac Disease)

- Vegetarians, vegans or patients with religious dietary restrictions (as the standard meal contains meat)
- Participant taking any glucose-containing medication concurrently

8. TRIAL PROCEDURES

8.1. Recruitment

The clinical diabetes team in each participating hospital will identify children in the service who are using multiple daily injections to manage their diabetes and who would be eligible for the study. In addition, in Oxford, an e-mail will be sent to all eligible patients' families signed up to the e-mail service to alert them that the study is open to recruitment. In Oxford, the study will be advertised generally in the routine 3 monthly newsletter which is available in the clinic, with details of who to contact for more information about the study. Once the family has expressed an interest in hearing more about the study, the participant and parent information sheet will be given to eligible children and young people and their parents at their routine diabetes clinic visit or sent in the post if interest has been expressed.

The information sheets will provide contact details of the researchers if the potential participants want more information before making a decision. After allowing a week for the child and parent to read the information sheets, the research nurse or dietitian will telephone the family asking if they have any further questions about the study, to provide further information, and enquire if the child and family are willing to consent. If they are willing to participate, an appointment will then be made to obtain informed consent.

8.1. Screening and Eligibility Assessment

The HbA1c level taken at the preceding clinic (maximum of 3 months before approach) will be used to assess eligibility. If the clinic visit was more than 3 months before the start of the study, a further HbA1c level will be measured by rapid analysis at the time of the first visit. All other screening and eligibility assessments can be carried out on the telephone by the research nurse or research dietitian.

8.2. Informed Consent

Informed consent will be undertaken by a nurse or doctor on the research or clinical team who has had GCP training with specific training in informed consent and has been authorised to do so by the Chief Investigator. Verbal and written information will be given to potential participants detailing no less than: the exact nature of the study; what it will involve for the participant; the implications and constraints of the protocol; and any risks involved in taking part. It will be clearly stated that the participant is free to withdraw from the study at any time for any reason without prejudice to future care, and with no obligation to give the reason for withdrawal. Information will be presented to children and young people both verbally and in written form in an age- appropriate manner. Written assent will be sought from children 8-16 years of age.

The participant will be allowed as much time as wished to consider the information and will be given the opportunity to question the doctor or nurse, their consultant, their GP or other independent parties to decide whether they will participate in the study.

Written Informed Consent will then be obtained by means of parent/legal guardian dated signature and dated signature of the person who presented and obtained the Informed Consent. A copy of the signed Informed Consent will be given to the participant. The original signed form will be retained at the study site. For children >8 years of age a dated signature will be sought on an assent form. Young people over the age of 16 will be able to sign their own consent form.

The parent/legal guardian or young person over the age of 16 must personally sign and date the latest approved version of the informed consent form before any trial specific procedures are performed.

8.3. Randomisation, blinding and code-breaking

Randomisation is required only for the order of the insulin dosing. The study statistician will provide the randomisation codes and the study dietitian will make up sealed envelopes with all the instructions inside for the schedule for the participant according to the randomised order of treatment. This schedule will form part of the study diary for each participant. The envelopes will be kept in the research office in Oxford until they are needed, when the next one will be taken for the next participant entering the study at any of the participating sites. The envelope will be opened by the research nurse or dietitian at the first study visit when the CGM is being inserted. As the same research team will be working at all sites there is no requirement for separate codes for each site.

Unblinding will not be required as this is not a blinded study. Participants and researchers will know the order of the insulin doses for the test meal from the start of the study.

8.4. Baseline Assessments

At visit 1, after the informed consent and assent forms have been signed, the dietitian will collect details of the insulin to carbohydrate ratios currently being used at the evening meal-time. A record book will be provided to the child and family to record their blood glucose levels, carbohydrate quantities and insulin doses for the run-in week. During the run in week the participant will be requested to record blood glucose levels before and 2 hours after meals, snacks and before bed. They will also be asked to record CHO intake and insulin doses given.

After 3 days the dietitian will telephone to obtain BG levels and work out whether any adjustments need to be made to the ratios. A further telephone call will be made on day 5-6, with further adjustment if necessary. After this first visit, the study meals will be ordered by the dietitian or nurse to be delivered to the participant's home.

